3.4 Randomization, Replacement, and Unblinding Procedures

Randomization will take place at the Baseline visit prior to first dosing. Subjects who meet all eligibility criteria will be randomized at a 2:1 ratio (drug:vehicle) to receive Roflumilast cream 0.15% QD or matching vehicle QD. The randomization will be stratified by vIGA-AD score at baseline ('Mild' vs. 'Moderate') and by study site according to a computer-generated randomization list. Kits containing tubes of study medication will be assigned to each subject using an internet-based response system (IWRS). A subject may receive more than one kit for the treatment period. The kits and tubes are blinded and each kit is numbered with a unique kit number.

The study is double-blinded, therefore neither the subjects nor the Investigator, sponsor and clinical personnel will be aware of which treatment an individual subject receives.

	STATISTICAL ANALYSIS PLAN, Version 3.0
Protocol Number: ARQ-151-311	Sponsor: Arcutis Biotherapeutics, Inc.

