5.1 Sample Size

There are approximately 650 subjects planned for this study. In order to have the desired power for the secondary endpoint of vIGA-AD Success in subjects with a vIGA-AD score of ‘Moderate’ at randomization, approximately 490 of the subjects to be accrued will have vIGA-AD score of ‘Moderate’ at randomization. Randomization will be stratified by vIGA-AD score (‘Mild’ vs. ‘Moderate’) and by study site.

The sample size of 650 subjects provides approximately 95% power to detect an overall 15% difference (Odds Ratio = 2.1) between treatment groups on vIGA-AD success at Week 4 at $\alpha=0.05$ using a 2-sided stratified Cochran-Mantel-Haenszel (CMH) test. The results from a recent Phase 2 study (ARQ-151-212) of Roflumilast cream 0.15% compared to vehicle treatment were used to estimate the treatment difference. Specifically, in the Phase 2 trial, approximately 37% of subjects demonstrated vIGA-AD Success at Week 4 in the ARQ-151 0.15% group compared to 22% in the vehicle group. The sample size of 490 also provides approximately 90% power to detect an overall 17% difference (Odds Ratio = 2.1) between treatment groups (28% of vIGA-AD Success at Week 4 in vehicle treatment) on vIGA-AD Success at Week 4 among subjects with vIGA-AD score ‘moderate’ at randomization. The same testing method, the stratified CMH test, will be used as for the primary endpoint.

To control for familywise type I error at level of 0.05, the secondary endpoint of vIGA-AD Success at Week 4 in subjects with vIGA-AD of ‘Moderate’ at randomization will only be tested if the primary endpoint demonstrates statistical significance. In addition, the remaining secondary endpoints will be inferentially tested only if the primary and secondary endpoint (vIGA-AD Success at Week 4 for subjects with vIGA-AD score of ‘Moderate’ at randomization) comparisons are statistically significant using the hierarchical testing procedure by partitioning of alpha (see Section 6.5 for more details).

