from the analysis of each multiply-imputed dataset will be transformed as per Wilson-Hilferty² before being combined using PROC MIANALYZE based on Rubin's rule. Because the Wilson-Hilferty transformation is a monotone transformation, the p-value for the CMH test is the one-sided p-value from the t distribution. This p-value will be the primary p-value used to evaluate the result according to the multiple testing strategy described in Section 6.5.

- i. Should the common MH odds ratio from the analysis of at least one of the multiply-imputed datasets be not estimable, combined common MH odds ratio and associated combined common 95% CI and p-value will not be presented. Under such circumstance, conclusions will be based on the p-value obtained from a multiple imputation test of the proportion difference, where the common proportion difference using MH weights and associated common standard errors based on the Sato variance estimator obtained from the analysis of each multiply-imputed dataset will be combined using PROC MIANALYZE based on Rubin's rule.

Similar multiple imputation method will be used for the average weekly WI-NRS and EASI total score.

For the average weekly WI-NRS (refer to Section 5.5), it's the missing average weekly WI-NRS data (i.e., those that cannot be computed because only 3 or less non-missing assessments are available during a given week) at Weeks 1, 2, 3, and 4 that will be multiply imputed, not the missing daily WI-NRS data. Since the missing average weekly WI-NRS values have a precision of 1 decimal place, the MCMC imputation for the non-monotone missing data will be restricted to values between 0 and 10, rounded to the 1st decimal (i.e., 0.1). Imputation of missing data for WI-NRS will be based on the ITT population, i.e., all randomized subjects will be included in the imputation process.

For the EASI total score (refer to Section 5.5), it's the missing EASI total score data at Weeks 1, 2, and 4 that will be imputed, not the missing EASI question score data. Since the missing EASI total scores have a precision of 1 decimal place, the MCMC imputation for the non-monotone missing data will be restricted to values between 0 and 72, rounded to the 1st decimal (i.e., 0.1). Imputation of missing data for EASI total score will be based on the ITT population.

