6.5 Multiple Comparisons/Multiplicity

To control for familywise type I error at level of 0.05, the secondary endpoint of vIGA-AD Success at Week 4 for subjects with vIGA-AD score of ‘Moderate’ at randomization will only be tested if the primary endpoint demonstrates statistical significance. In addition, the remaining secondary endpoints will be inferentially tested only if the primary and the secondary endpoint (vIGA-AD Success at Week 4 for subjects with vIGA-AD score of ‘Moderate’ at randomization) comparisons are statistically significant using hierarchical testing procedure by partitioning of alpha.

Upon successful demonstration of statistical significance for the primary and above secondary endpoint, the remaining endpoints will be grouped into secondary endpoint family 1, comprised of the 4-point reduction on the WI-NRS endpoint, at Week 4, Week 2 and Week 1, and secondary endpoint family 2, comprised of the endpoints of EASI-75 at Week 4, vIGA-AD of ‘clear’ or ‘almost clear’ at Week 4, vIGA-AD of success at Week 2 and Week 1, vIGA-AD of ‘clear’ or ‘almost clear’ at Week 2 and Week 1. An alpha level of 0.03 will be used to test the endpoints in the secondary endpoint family 1 sequentially. An alpha level of 0.02 will be used to test the endpoints in secondary endpoint family 2 sequentially.

	STATISTICAL ANALYSIS PLAN, Version 3.0
Protocol Number: ARQ-151-311	Sponsor: Arcutis Biotherapeutics, Inc.

In addition to the partitioning of the overall 0.05 alpha into two families, the Fallback Method will be applied. The fallback method is a modification of the fixed-sequence method, providing opportunity to test an endpoint later in the sequence even if an endpoint tested early in the sequence has failed to show statistical significance. The order of the endpoints remains important. The appeal of the fallback method is that if an endpoint later in the sequence has a robust treatment effect while the preceding endpoint is unsuccessful, there is a modest amount of alpha retained as a fallback to allow interpretation of that endpoint without inflating the Type I error rate. Applying the fallback method begins by dividing the total alpha (not necessarily equally) among the endpoints and maintains a fixed sequence for the testing. In this study, the Fallback Method will be applied to the fixed sequence of testing Family 1, and then Family 2.

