12.1.3 Primary Endpoint Analysis

For the primary analysis, missing vIGA-AD scores will be imputed using multiple imputation as described in Section 6.2.1. These imputations will result in a minimum of 25 to a maximum of 250 complete analysis datasets, depending on the number of imputed monotone datasets that are required.

Percentages of subjects having a vIGA-AD Success (refer to Section 12.1.1) will be presented by visit and treatment group based on multiply imputed data in the ITT population along with a 95% Wilson CI. The common MH odds ratio and common MH proportion difference, adjusted for the randomization factors (i.e., randomized vIGA-AD score and pooled study site) will also be provided along with their common associated 95% CIs. Additionally, count and percentage of subjects having a vIGA-AD success, count and percentage of subjects in each category of the vIGA-AD scale, and descriptive statistics for the vIGA-AD scores, change in vIGA-AD score from

	STATISTICAL ANALYSIS PLAN, Version 3.0
Protocol Number: ARQ-151-311	Sponsor: Arcutis Biotherapeutics, Inc.

baseline and percent change in vIGA-AD score from baseline will be presented by visit and treatment group based on observed data in the ITT population.

The primary endpoint (vIGA-AD Success at Week 4) will then be analyzed using multiple imputation CMH test stratified by the randomization factors. To do so, a CMH analysis will be performed separately for each of the complete multiply imputed analysis data sets, and results will be combined into one multiple imputation inference using the methodology described in Section 6.2.1. Statistical significance will be concluded at the 5% significance level (2-sided). Should the odds ratio be not estimable for at least one multiply imputed dataset, the conclusion of the study will be based on the p-value obtained from a MH test, stratified by the randomization factors, for the common MH proportion difference at Week 4.

The following sensitivity analyses to the primary analysis of the primary endpoint will be performed:

- Multiply-imputed data (refer to Section 6.2.1) on mITT population (refer to Section 4.2) and
- Tipping Point analysis (refer to Section 6.2.3) on ITT population.
- Non-responder imputation (refer to Section 6.2.2) on ITT population.
- Observed data on ITT population (refer to Section 4.1).
- Observed data on PP population (refer to Section 4.3).

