For each categorical exploratory efficacy endpoint, count and percentages of subjects meeting the criteria for an exploratory efficacy endpoint will be presented by visit and treatment group based on observed data in the ITT population along with a 95% Wilson CI. Additionally, count and percentage of subjects meeting the criteria for vIGA-AD of Clear (0), EASI-50, EASI-90, and EASI-100 at Week 1 and Week 2 will also be presented by visit and treatment group based on observed data in the ITT population along with a 95% Wilson CI.

Continuous exploratory efficacy endpoints will be analyzed at Week 1, Week 2, and Week 4 and for daily WI-NRS assessments using an analysis of covariance (ANCOVA) with the factors of treatment, two stratification variables (pooled study site and randomized vIGA-AD score), and baseline of the variable under analysis as covariate. Statistical comparisons between the treatment groups will be obtained using contrasts. The Least Square (LS) mean and its standard error, difference in LS means between treatment group (i.e., active - vehicle), its standard error and associated 95% confidence interval, and p-value for difference from vehicle will be presented at each visit. These analyses will be performed based on observed data in the ITT population.

Categorical exploratory efficacy endpoints at Weeks 1, 2, and 4 will be analyzed using a CMH test adjusted for the two stratification variables (pooled study site and randomized vIGA-AD score). Common MH odds ratio, common MH proportion difference and their common associated 95% CI, adjusted for the randomization factors, will be provided. The p-value will be from a CMH test for the common MH odds ratio, unless the common MH odds ratio is not estimable. In such circumstances, the p-value will be from a MH test for the common MH proportion difference.

The analysis of these endpoints will be performed on the observed data with no imputation. The p-values will be nominal as no formal inferential testing will be done on exploratory efficacy endpoints.

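### When the odds ratio is not estimable in even one imputed dataset, the SAP replaces the CMH test by a Sato-variance difference test: unnecessary, and too liberal for low-rate secondary endpoints

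*SAP*

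**What the plan says.** SAP 6.2.1 step 3c names the pooled CMH p-value (Wilson-Hilferty transformed, combined by Rubin's rule) as the one used in the multiple testing strategy. It then adds an exception. If the common MH odds ratio is not estimable in at least one of the 25 to 250 imputed datasets, the odds ratio, its interval and its p-value are not shown, and "Under such circumstance, conclusions will be based on the p-value obtained from a multiple imputation test of the proportion difference", with MH weights and Sato standard errors.

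SAP 12.1.3 repeats this for the primary endpoint: "Should the odds ratio be not estimable for at least one multiply imputed dataset, the conclusion of the study will be based on the p-value" of the proportion-difference test. SAP 12.2 analyses Family 1 as in 12.1.3 and Family 2 as in 6.2.1, so the exception reaches every alpha-controlled secondary endpoint. SAP 12.3 has the same switch for exploratory endpoints: "In such circumstances, the p-value will be from a MH test for the common MH proportion difference". The p-values there are declared nominal.

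SAP 6.5 claims familywise control at 0.05. On the families it says: "An alpha level of 0.03 will be used to test the endpoints in the secondary endpoint family 1 sequentially", and "An alpha level of 0.02 will be used to test the endpoints in secondary endpoint family 2 sequentially". Family 2 moves to 0.05 if all of Family 1 succeeds. No reason is given for setting the CMH p-value aside.

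**The concern.** The exception treats failure of an estimate as failure of a test. The CMH statistic is built from observed-minus-expected counts and a hypergeometric variance. It does not use the odds ratio, and it is defined as soon as one stratum holds both arms and both outcomes.

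The replacement is also weakest where it is called on. The MH odds ratio breaks down when no stratum has both a vehicle success and an active failure, which in practice means no vehicle successes. The Sato standard error then carries almost no uncertainty from the vehicle arm.

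At stake are the low-rate endpoints inside the alpha scheme. vIGA-AD Success at Week 1 requires a Mild subject to become clear within about a week. WI-NRS response at Week 1 requires a 4-point fall in the average over days 1-7, in a restricted subset aged 12 or older. A false pass on WI-NRS Week 1 would release 0.03 to Family 2. A false pass on vIGA-AD Success at Week 1 would open two further endpoints.

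**Working it through.** **Inputs from the SAP.** "There are approximately 650 subjects planned for this study" (5.1). Allocation is 2:1 (3.4), giving about 433 active and 217 vehicle. The Moderate subset is 490, so about 163 vehicle. Vehicle rates are 22% and 28% (5.1). Alpha is 0.05, 0.03 or 0.02 (12.1.3, 6.5). Site pools hold at least 16 subjects (6.4).

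**Assumed, because the documents give nothing:** a common null success rate of 0.25% to 3% for an early endpoint, the stratum layout, and a WI-NRS population of 300.

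The SAP has no figure for how this rule performs, so there is none to reproduce. (Its 95% power figure comes out at 97.9% by a simple two-proportion formula, but that does not bear on this point.)

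**1. The two statistics with x active and 0 vehicle successes, single stratum.**

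CMH: E = x·n1/N, V = n1·n0·x·(N−x)/[N²(N−1)], χ² = (x−E)²/V. For x = 5: E = 3.331, V = 1.105, χ² = 2.521, p = 0.112.

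Sato: δ = x/n1, variance = (δP + Q)/W². With no vehicle successes, P = [−n0²x + n1·n0(n0−n1)/2]/N², Q = x·n0/(2N), W = n1·n0/N. For x = 5: δ = 0.01155, P = −24.58, Q = 0.8346, W = 144.56, SE = 0.00513, z = 2.249, p = 0.0245.

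In general the Sato variance is about x/n1², so z² ≈ x. Under 2:1 the CMH χ² is about (x/3)²/(2x/9) = x/2. The replacement roughly doubles the chi-square.

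| Successes | CMH p | Sato p |
|---|---|---|
| 4 vs 0 | 0.156 | 0.0445 |
| 5 vs 0 | 0.112 | 0.0245 |
| 6 vs 0 | 0.082 | 0.0136 |
| 8 vs 0 | 0.044 | 0.0043 |

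Given 4 successes in all, the null chance that all fall in active is 0.196, yet Sato calls this significant at 0.05. At 0.02, Sato needs 6 vs 0 and CMH needs 11 vs 0.

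**2. How often the switch would fire.** The chance of no vehicle success is (1−p)^n0. Primary: 0.78^217 = 4×10⁻²⁴. Moderate: 0.72^163 = 6×10⁻²⁴. For 217 vehicle subjects at true rates of 0.5%, 1%, 2% and 3%, it is 34%, 11%, 1.2% and 0.13%.

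**3. Null rejection rate with complete data.** Simulation with 30 pooled sites × 2 severities and 180,000 trials per rate. Zero active successes (log odds ratio undefined) also count as a trigger. Each cell gives the SAP rule, then CMH throughout.

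| Rate in both arms | α = 0.05 | α = 0.03 | α = 0.02 |
|---|---|---|---|
| 0.75% | 9.1% / 3.7% | 5.4% / 2.0% | 2.7% / 1.3% |
| 1% | 9.3% / 4.1% | 6.2% / 2.1% | 3.9% / 1.4% |
| 1.5% | 6.6% / 4.7% | 4.6% / 2.5% | 3.6% / 1.6% |
| 2% | 5.1% / 4.7% | 3.3% / 2.7% | 2.5% / 1.8% |
| 3% | 4.9% / 4.9% | 2.8% / 2.8% | 1.9% / 1.9% |

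At 0.5% the SAP rule gives 6.1% at α = 0.05 but is below nominal at 0.03 and 0.02. At 0.25% and α = 0.05 it gives 1.3%. The excess favours active: at a 1% rate and α = 0.05, rejections in that direction rise from 0.9% to 6.6%.

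The size depends on layout. At 1%, 40 pools of 12 Moderate and 4 Mild gave 0.076/0.047/0.031 at the three alphas. Fixing the arms within each pool at 8:4 and 3:1 gave 0.110/0.079/0.051. CMH stayed below nominal in both. In an assumed WI-NRS set of 300 at a 3% rate, the rule gave 0.041 at its applicable 0.03.

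**4. With imputation.** Using 25 imputations, 5% or 10% missing, a simplified Beta-Bernoulli imputation in place of predictive mean matching, and a 1% rate, the SAP rule gave 4.3% to 8.9% at nominal 0.05 and CMH gave 2.6% to 4.5%. The lowest figure, 4.3%, came with 10% missing imputed from a pooled rate. There the switch fired in 14.8% of trials, and in 14.1% it fired in only some of the datasets.

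**The case against.** The strongest reply is about reach, and most of it stands. The two tests that gate everything else cannot realistically trigger the switch. The affected band is narrow: in ITT the rule and CMH agree at 3% or more, and no document says that any Week 1 rate lies below that. WI-NRS Week 1 is third in Family 1 and vIGA-AD Success Week 1 is fourth in Family 2, so several endpoints must succeed first. The 5 vs 0 example would not pass at Family 2's initial 0.02; 6 vs 0 would. Missing data add between-imputation variance, which in one setting brought the rule back within 5%. If zero active successes also count as non-estimable, Sato is more conservative than CMH in that tail, which offsets part of the excess at the lowest rates.

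Three stronger readings should be resisted.

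- Because 12.1.3 speaks of the study's conclusion, a reader might infer that the primary result is exposed. At a 22% vehicle rate it is not.
- A reader might infer that familywise error exceeds 0.05. The figures here are per test; no familywise rate under the gated sequence has been computed.
- A reader might infer that one failed dataset out of 250 makes the p-value far too small. That is clear only when all or nearly all datasets lack vehicle successes. When only some do, the others contribute vehicle events and between-imputation variance.

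None of this defends the switch itself. Where the CMH p-value can be computed, replacing it gains nothing. Gating also protects little if the cream works at Week 4 but not yet at Week 1.

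**Conclusion.** The point holds in limited form and merits a should-fix. The rule is unnecessary, and it is anti-conservative when vehicle has no successes. It has no practical effect on the Week 4 primary or Moderate endpoints at the planned rates.

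It can inflate the per-test type I error of an alpha-controlled secondary endpoint whose success rate is about 0.5-2% in ITT, or about 1-3% in an assumed WI-NRS population of 300. At an assumed 1% ITT rate with complete data, the size is about 0.08-0.11 at nominal 0.05, 0.05-0.08 at 0.03 and 0.03-0.05 at 0.02, depending on stratum layout. Imputation lowers this. Whether any endpoint falls in the band cannot be known from the documents. The exploratory p-values in 12.3 carry no error-rate claim, so nothing is at stake there.

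**What to change.** In SAP 6.2.1 step 3c and 12.1.3, replace the switch with wording such as:

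*The multiple-imputation CMH p-value decides every primary and secondary endpoint whenever it can be computed, whether or not the MH odds ratio is estimable. If the odds ratio is not estimable, it is reported as NE, and the MH proportion difference with its confidence interval is given as the estimate only.*

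Section 12.2 then inherits the change by reference. Aligning 12.3 is optional, for consistency. The cost is SAP wording and the removal of one programming branch; no data collection, sample size or alpha allocation changes.

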6.2.2 Non-responder Imputation Analysis

If assessment of vIGA-AD after baseline is missing, the subject will be considered as non-responder (for example, no vIGA-AD success in the analysis of vIGA-AD success). For the vIGA-

	STATISTICAL ANALYSIS PLAN, Version 3.0
Protocol Number: ARQ-151-311	Sponsor: Arcutis Biotherapeutics, Inc.

AD success endpoints, subjects with missing baseline vIGA-AD score will be considered as non-responder for these endpoints only. That is, for the secondary efficacy endpoints of vIGA-AD score of clear (0) or almost clear (1) and vIGA-AD score of clear (0), the post-baseline assessment at a specific visit will be established based on the vIGA-AD score at that visit only, regardless of the availability of the baseline vIGA-AD score.

Similar imputation method will be used for 4-point reduction on the average weekly WI-NRS and EASI-75. For EASI-75, subjects with missing baseline EASI total score will be considered as non-responder. For 4-point reduction on the average weekly WI-NRS, subjects with missing baseline average weekly WI-NRS will not be imputed since the analysis of WI-NRS endpoints will be performed based on the WI-NRS population from which subjects with a missing baseline average weekly WI-NRS are excluded.

6.2.3 Tipping Point Analysis

As a sensitivity analysis to the multiple imputation analysis as described in Section 6.2.1 for the vIGA-AD success primary endpoint and secondary endpoint of vIGA-AD success among subjects with Moderate disease at baseline, a tipping point analysis will be performed in order to determine the inflection point at which the inference under the missing not at random (MNAR) assumption changes substantially.

The sensitivity analysis for the primary endpoint will be performed by using a specified sequence of shift parameters. The range of shift parameters to be included in this analysis are 0 to 2 by 0.2 for active and -2 to 0 by 0.2 for Vehicle. The values at which the results of the primary analysis are shifted from significant (i.e., $\alpha \leq 0.05$) to non-significant (i.e., $\alpha > 0.05$) will be determined. Steps 1 and 3 of the analysis will be the same as for the multiple imputation analysis as described in Section 6.2.1. However, Step 2 of the analysis is where the shift parameters will be applied.

Imputed values for subjects who discontinue due to lack of efficacy or adverse event will be handled as described in Step 2 of Section 6.2.1 to ensure that these subjects are analyzed as non-responders at all visits on or after discontinuation of treatment.

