6.2.1 Multiple Imputation

All subjects, regardless of completion status, will have available data assigned to the pre-specified analysis visit using the analysis windows defined in Section [5.4](#), including the last available data

	STATISTICAL ANALYSIS PLAN, Version 3.0
Protocol Number: ARQ-151-311	Sponsor: Arcutis Biotherapeutics, Inc.

of subjects who prematurely withdraws from the study. To comply with the definition of the primary estimand (Section 12.1.1), for subjects who discontinue due to lack of efficacy or adverse event, efficacy data assigned to a pre-specified analysis visit will be removed from the source data used for the multiple imputation process if subject's last dose day falls within the analysis visit window or is prior to the start of the analysis visit window used to assign data to a pre-specified analysis visit. Similarly, WI-NRS weekly averages will be removed from the source data used for multiple imputation if subject's last dose day falls within the analysis visit window or is prior to the start of the interval used to compute the weekly average as defined in Section 5.4. This procedure will ensure that the data collected on or after intercurrent events are not used in the imputation process.

For the primary efficacy endpoint of vIGA-AD success at Week 4 and the secondary endpoint of vIGA-AD success at Week 4 among subjects with a 'Moderate' randomized vIGA-AD score, the primary analysis will impute missing values using a Predictive Mean Matching (PMM) sequential-regression multiple imputation model for the ITT population. This is a three-step process.

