1. The first step is to understand the pattern of missingness. In order to perform the multiple imputation, a monotone missing pattern has to be achieved. For example, if there exist values for baseline and Week 4 visits, but missing values for the Week 1 or 2 visits, the Markov-Chain Monte-Carlo (MCMC) method will be used to impute the small amount of missing data that may be missing at the intermediate visits that is required to make the missing data pattern monotone before applying the multiple imputation algorithm. This method uses a non-informative Jeffreys prior to derive the posterior mode from the expectation-maximization (EM) algorithm as the starting values for the MCMC method. The MCMC method will use the seed 6457149. The vIGA-AD score will be treated as a continuous variable for this step and the model will include the vIGA-AD scores at baseline, Week 1, Week 2, and Week 4. To avoid values that could not be observed in practice, imputed values will be rounded to the nearest integer (Round=1 option in PROC MI) in the range of 0 to 4.

To determine the number of multiply-imputed datasets to be created at this step, the proportion of datapoints with non-monotone pattern across all visits and subjects will first be derived as follows:

$$\frac{\text{number of non monotone visits accross all visits and subjects}}{\text{total number of expected visits across all subjects}} * 100$$

Then, the following table will be used:

	STATISTICAL ANALYSIS PLAN, Version 3.0
Protocol Number: ARQ-151-311	Sponsor: Arcutis Biotherapeutics, Inc.

Non-monotone Missing Data	Number of Imputed Datasets
$\leq 2\%$	1
$> 2\% \text{ to } \leq 5\%$	3
$> 5\%$	10

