2. Once the monotone pattern is achieved, the next step is to implement the imputation algorithm. For this, the PMM regression method will be used. This method is particularly helpful if the normality assumption is violated. For subjects with complete data up to a particular visit, a PMM regression model will be fit that includes the outcome at that visit as the dependent variable and as independent variables, the treatment group, pooled study site, and vIGA-AD score outcomes at previous visits, using a seed of 482371. For other scales/questionnaires, the actual baseline vIGA score will also be included as an independent variable. This process will be repeated 25 times, resulting in a total of 25 to 250 complete analysis datasets, depending on the number of imputed monotone datasets that are required. The seed may be changed after unblinding in case of any issues with the imputation process, and it will be documented in the CSR if any change is required.
3. For each of the 25 to 250 completed dataset, the necessary derived variable will be computed as defined in Section 5.5 and analyzed using a CMH analysis, adjusted for the pooled study site and randomized vIGA-AD score for the primary efficacy endpoint and adjusted for the pooled site for the secondary efficacy endpoint. Results will be combined into one multiple imputation inference as follows:
 - a. Common proportion of success, common Mantel-Haenszel (MH) proportion difference (and associated 95% CI), and common MH odds ratio (and associated common 95% CI) will be combined using PROC MIANALYZE based on Rubin's rule. Common MH odds ratios and associated common 95% CI will first be normalized using a log-transformation before being combined using PROC MIANALYZE. The resulting combined common MH odds ratio and associated combined common 95% CI will be back-transformed to the arithmetic scale before being presented in a table.
 - b. For the combined common proportion of success, the associated combined common 95% CI will be calculated as per Lott and Reiter multiple imputation Wilson interval method¹.
 - c. Two p-values will be produced for each analysis:
 - i. The primary p-value will be obtained from a multiple imputation CMH test, where CMH general association statistics and their standard errors obtained

	STATISTICAL ANALYSIS PLAN, Version 3.0
Protocol Number: ARQ-151-311	Sponsor: Arcutis Biotherapeutics, Inc.

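### Does SAP 6.2.3 need changing because it does not say how 0.2-step shifts act on an integer vIGA-AD score?

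*SAP*

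**What the plan says.** SAP 6.2.3 plans a tipping-point analysis for vIGA-AD success at Week 4, in the full ITT population and in subjects with Moderate disease. It states that "The sensitivity analysis for the primary endpoint will be performed by using a specified sequence of shift parameters", and that these parameters "are 0 to 2 by 0.2 for active and -2 to 0 by 0.2 for Vehicle". Steps 1 and 3 of the multiple imputation in 6.2.1 are kept; "Step 2 of the analysis is where the shift parameters will be applied". The result to be reported is described as "The values at which the results of the primary analysis are shifted from significant" to non-significant.

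Step 2 in 6.2.1 is sequential predictive mean matching, with predictors "the treatment group, pooled study site, and vIGA-AD score outcomes at previous visits". The only rounding rule for vIGA-AD belongs to Step 1, the MCMC fill-in of intermediate visits: "imputed values will be rounded to the nearest integer (Round=1 option in PROC MI) in the range of 0 to 4". Step 3 applies the success definition in Section 5.5 (score 0 or 1 and an improvement of two grades or more), and Section 12.1.1 says the scale takes whole numbers only.

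For subjects who stop because of an adverse event or lack of efficacy, 6.2.3 says their imputed values "will be handled as described in Step 2 of Section 6.2.1". The working rule is in fact in the opening of 6.2.1, where "efficacy data assigned to a pre-specified analysis visit will be removed from the source data used for the multiple imputation process" once the last dose falls in or before the visit window, and in Section 5.5, which sets these subjects to non-success.

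**The concern.** A tipping-point analysis delivers one thing: how far imputed outcomes must be moved before significance is lost. Here the move is in fifths of a grade, while the outcome is a whole-number score cut at a threshold. If the shift is added to the score drawn from a donor, most of the 11 steps change nobody's responder status, and the step at which status does change depends on whether the shifted score is rounded.

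Unrounded, an active-arm donor score of 1 becomes 1.2 and fails at the very first step, whereas a vehicle donor score of 2 has to fall by a full grade before it counts as success. A reader could take a tipping value of 0.2 as fragile and 0.6 as sturdier, although both may describe the same reclassification. This is the only listed sensitivity analysis of the primary endpoint that varies a departure from the imputation model over a range, so it is fair to ask for its rule to be fixed before unblinding. The reference to Step 2 for discontinuations, which holds no such rule, adds to the impression of an unfinished section.

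**Working it through.** **Inputs.** Grid from SAP 6.2.3: (2 - 0)/0.2 + 1 = 11 shifts per arm. Score from 12.1.1: whole numbers 0 to 4. Baseline b = 2 or 3, from the entry criteria. Success from 5.5: score y ≤ 1 and b - y ≥ 2, which means y ≤ 0 for Mild and y ≤ 1 for Moderate. The SAP states no tipping value to reproduce.

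**Shift of size s added to the drawn Week 4 score d only** (y = d + s active, y = d - s vehicle):

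| Coding | Arm | No change | One grade | Two grades | Steps in each |
|---|---|---|---|---|---|
| Unrounded | Active | 0 | 0.2 to 1.0 | 1.2 to 2.0 | 1/5/5 |
| Unrounded | Vehicle | 0 to 0.8 | 1.0 to 1.8 | 2.0 | 5/5/1 |
| Rounded, 0 to 4 | Both | 0 to 0.4 | 0.6 to 1.4 | 1.6 to 2.0 | 3/5/3 |

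Example, active, b = 3: d = 1 fails once 1 + s > 1, at s = 0.2; rounded, it fails once 1 + s rounds to 2, at s = 0.6. For d = 0 the limits are 1.2 and 1.6. Vehicle, b = 3, d = 2 succeeds once 2 - s ≤ 1, at s = 1.0; rounded, at s = 0.6. No multiple of 0.2 ends in .5, so the tie rule does not matter. In Mild active subjects only d = 0 succeeds, so the one-grade and two-grade columns coincide and there are two patterns.

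**Crossed arms.** 3 × 3 = 9 scenarios, and they are the same nine under either coding. At the far corner (active +2.0, vehicle -2.0) both codings give two grades in each arm.

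**Paired arms (equal and opposite shifts).** Unrounded: five scenarios (0; 0.2 to 0.8; 1.0; 1.2 to 1.8; 2.0). Rounded: three (0 to 0.4; 0.6 to 1.4; 1.6 to 2.0). Here the scenarios tested differ as well as the labels.

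**Shift before matching.** The imputed value is still an observed whole-number score, so Step 3 needs no extra rule and the three-pattern collapse does not arise.

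**A fully literal reading** (the shifted score must equal exactly 0 or 1) makes an active b = 3, d = 0 subject fail at 0.2 to 0.8, succeed at 1.0 and fail again afterwards. That is visibly wrong, and an analyst would discard it.

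**Illustration with assumed effects and missingness** (650 subjects, 2:1, 25 imputations, paired shifts). First shift with p > 0.05:

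| Missing | Observed success, active vs vehicle | Before matching | Unrounded | Rounded |
|---|---|---|---|---|
| 10% | 37.4% vs 27.0% | 0.2 | 0.2 | 0.6 |
| 10% | 44.4% vs 27.0% | 0.8 | 1.2 | 1.6 |
| 5% | 42.0% vs 28.0% | 1.4 | 1.2 | 1.6 |
| 15% | 47.2% vs 20.9% | none | none | none |

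In the last row p at shift 2.0 is 0.0305 before matching and 0.0388 under both codings after matching. In these four datasets the label moves, but the three workable readings agree on whether significance is lost within the grid.

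**Limit of the enumeration.** It holds Weeks 1 and 2 unshifted. If unrounded shifts are added at every imputed visit, each step also changes the predictors of Week 4. One illustrative run (assumed 10% missing at Week 4, about half of those also missing Weeks 1 and 2) then gave 4 active and 8 vehicle patterns in place of 3 and 3. The counts above therefore belong to one reading.

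**The case for a change.** The best argument for a change is that the tipping value is itself the reported result, so a label that depends on coding is a result that depends on coding. In the first illustrative dataset the same data give 0.2 or 0.6, and with paired shifts the two codings do not test the same scenarios. Section 6.2.1 names a software option for rounding in Step 1; 6.2.3 gives nothing comparable for the shift. Settling this takes a few sentences and no new data.

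The silence is real, and so is the dependence of the label on coding. Less of the rest stands. Separate ranges for each arm, and a result described in the plural, point to a two-way grid, where the codings cover identical scenarios. The Moderate subset has no missing grid: 6.2.3 opens by naming both endpoints, and Section 12.2 sends the Moderate analysis back to 6.2.3, which contains one grid. The Step 2 reference is a clerical slip, because 6.2.3 itself says these subjects are analysed as non-responders, and 6.2.1 and 5.5 make them so.

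The planned size of the Mild stratum is no measure of impact either. A shift moves only imputed scores, and early-termination or unscheduled data from Days 23 to 43 can fill Week 4 under Section 5.4. The obvious replacements, whole-grade shifts or shifts in response probability, are other methods on which statisticians could differ. Whole-grade shifts are also coarse: +1 already makes every imputed Mild active subject a non-responder.

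**Conclusion.** No change to the plan follows. Section 6.2.3 omits detail that an analyst must supply, but no rule it does state has been shown to give a wrong answer. The sensible implementations are easy to identify: shift before matching, or shift the drawn score, keep it within 0 to 4 and cross the arms. The choice can be recorded in the programming specification before unblinding. Reporting the implied response rate among imputed subjects at the boundary would make any label interpretable.

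At its largest the effect is on the label of one of the eight sensitivity analyses listed for the primary endpoint in Section 12.5: the same one-grade step is called active +0.2 or +0.6, and vehicle -1.0 or -0.6. That size assumes the shift is added to the drawn Week 4 score only. The primary test, its p-value and the handling of adverse-event and lack-of-efficacy discontinuations are unaffected. If the effect is large or little is missing, every reading may report no tipping, and the gap then has no consequence; the documents give no missing-data rate from which to judge this in advance.
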